### **7.4 Step 4. Post-treatment follow-up**

After completion of HCV treatment, all participants will have study visits at weeks 16 and 24 with evaluations as per Table 5. Visits must occur within the windows indicated on the schedule of events.

**Total study duration: Up to 30 weeks.**

Table 5: Step 3 and Step 4 Schedule of Events

Evaluation	Step 3 HCV Treatment with SOF/VEL				Step 4 Post-treatment Follow Up	
	Week 2 ± 3 days	Week 4 ± 3 days	Week 8 ± 3 days	Week 12 ± 3 days	Week 16 ± 5 days	Week 24 ± 5 days
Plasma Viral Kinetics (HCV RNA)	X	X	X	X	X	X
Concomitant Medication	X	X	X	X		X
Targeted Physical Exam				X		X
Stored PBMCs (Immunology)		X				X
Stored Plasma (Resistance)	X	X	X	X	X	X

## 8.0 Materials and Methods

### 8.1 Dosing

All doses of study treatment should be taken at or around the same time of day. During Step 2, subjects should not take their dose of study drug until after each pre-dose sample is obtained on VK days. Once the VK is obtained, each dose of study drugs will be taken orally with approximately 240 mL of water approximately 30 minutes after a meal or snack for Groups A, B, and C.

### 8.2 Dietary Requirements

Subjects will fast as directed by the radiology department on Entry/ Day 0 in preparation for CNB1. Upon return to the clinical research unit after CNB1, subjects receive a standardized diet on entry/day 0 that will provide approximately 40% of the daily calories from fat and up to 45% of the daily calories from carbohydrates (approximately 2200 calories/day). Snacks may be given ad lib with no restrictions on Day 0. On days 1-6, participants will have a diet ad lib.

### 8.3 Liver Fibrosis Staging

A sample of the core liver biopsy tissue from CNB1 will be sent for clinical evaluation of liver disease stage by the liver pathologist at the site (clinical care). Handling of this sample will occur as per Johns Hopkins Standard Operating Procedures (SOPs).

#### 8.4 Plasma Viral Kinetics (VK)

Plasma for VK will be collected for HCV RNA measurements at entry/day 0 (intensive sampling) and days 1, 2, 3, 4, and 7.

Upon admission to the inpatient research unit on Day 0, a peripheral IV will be placed or phlebotomy performed and the predose VK sample will be collected. After CNB1 is performed on entry/day 0, participants will be immediately returned to the inpatient unit and will receive a standardized meal. About 30 minutes after the meal is given, study drug will be administered. HCV RNA and plasma immunology measurements will be timed based on DAA administration, with DAA administration being considered Hour 0 for the VK portion of the study. Thereafter, intensive VK sampling over 24 hours will be conducted, with post-dose samples being collected at 4h, 6h, 12h, 18h, and 24h after drug administration.

After the 24-hour intensive plasma VK measurements are completed (on day 1), participants will be administered DAAs for day 1 and discharged to home. Thereafter, they will return daily for phlebotomy on days 2, 3, and 4 timed in relation to the intensive plasma VK samples performed on entry/day 0. Samples will be timed so that they are obtained  $24 \pm 2$  hours from the first administered dose of study drugs on entry/day 0 if this is possible based on the subject schedule. Phlebotomy will be performed for plasma VK (HCV RNA) measurements and plasma immunology measurements. DAA will be administered after phlebotomy on days 2, 3, and 4.

On day 7, participants will undergo phlebotomy for plasma VK (HCV RNA) measurements and plasma immunology measurements.

**Table 6: 24 Hour Intensive VK Specimen schedule for entry/Day 0 and Day 1 (*sample*)**

Study Assessment or Procedure	Expected Time	
	Day 0	Day 1
Admission to Osler 5	6:00	-
Place peripheral IV	6:15	
Collect predose blood sample	7:30	
Ambulatory or transport to liver biopsy	8:00	
Liver biopsy (CNB1)	9:00	
Vital signs and post-procedure site assessment- 0 hour post biopsy	9:30	
Stretcher transport return to Osler 5	10:00	
Administer standardized meal	10:30	
Vital signs and nursing assessment- 1 hour post biopsy	10:30	
Dosing of study drug with 240 mL of water 30 minutes after meal	11:00	
Vital signs and nursing assessment- 2 hour post biopsy	11:30	
Snack ad lib	11:00-15:00	
Collect 4 hr post-dose blood sample	15:00	
Administer standardized meal after 4 hr post-dose	15:15	

Collect 6 hr post-dose blood sample	17:00	
Administer standardized meal after 6 hr blood sample and before 12 hr blood sample	17:00-23:00	
Collect 12 hr post-dose blood sample	23:00	
Snack ad lib		00:00-10:30
Collect 18 hr post-dose blood sample		5:00
Administer standardized breakfast		10:30
Collect 24 hr post-dose blood sample		11:00
Dosing of study drug with 240 mL of water		11:00
Remove peripheral IV		11:15
Discharge subject from CRU		12:00

### 8.5 Stored PBMCs (Immunology)

PBMCs for immunology studies will be collected as outlined in the schedule of events. 10 mL of whole blood will be collected in a heparin tube and brought to the research lab for prompt processing.

### 8.6 Stored Plasma (Resistance)

A single plasma sample will be archived for analysis of viral resistance as outlined in the schedule of events. 10 mL of whole blood will be collected in an EDTA tube and brought to the research lab for prompt processing.

### 8.7 Core Needle Liver Biopsy

Core liver biopsy 1 will be performed in two passes or more as needed to obtain adequate tissue, and a technician will be present during the harvesting of liver tissue for prompt processing.

Core liver biopsy 2 will then be performed in one pass or more as needed to obtain adequate tissue, and a technician will be present during the harvesting of liver tissue for prompt processing.

### 8.8 Liver Tissue preparation and intra-hepatic VK analysis

#### An outline of single cell Laser Capture Microdissection (scLCM)

To address the mechanisms underlying HCV clearance, we will use several novel techniques to measure the number and the distribution of HCV-infected hepatocytes, intracellular immune responses, and intrahepatic drug concentrations. Single hepatocytes will be separately analyzed for their HCV RNA content and innate immune responses by integrating scLCM and quantitative PCR (qPCR). We will employ four major methodological advances to study the clearance rate of HCV-infected hepatocytes during DAA treatment: i) scLCM, ii) high-resolution

qPCR, iii) unbiased sampling with an integrated image bank to map the viroscapes, and iv) single-cell HCV Core-E1 sequencing.

**Tissue preparation.** Liver tissue is processed and placed on glass and polyethylene naphthalate (PEN) membrane slides while being kept at  $-24^{\circ}\text{C}$  for the duration of their pre-visualization time to preserve RNA. After staining, slides are stored at  $-80^{\circ}\text{C}$  until scLCM. RNase inhibitors such as RNeasy Protect are avoided as their high viscosity impedes scLCM.

**scLCM.** A Leica LMD 6500, laser microdissection system, was acquired by [name]. The instrument integrates a high-density photon laser with a fully motorized light microscope. Since bulk tissue analysis pools disparate signals, and tissue disruption with cell purification neglects anatomic context, conventional microdissection was developed to enrich cells of a given type for downstream analysis. Previous studies have required hundreds to thousands of cells. We have improved the technique by dissecting individual liver cells into separate containers, developing scLCM through rigorous testing and validation using liver samples from HCV-infected subjects [5, 8].

Hepatocytes are dissected from a 10mm 16-gauge segment of liver using the fully integrated Leica LMD 6500 system. Ten micro-thick tissue segments are cut and placed on a membrane, ethanol-fixed, and quick-stained with hematoxylin to reveal cell nuclei and hepatocyte morphology without compromising RNA recovery. Then, the UV-A diode-laser is focused through the microscope objective to achieve a spot size of less than 1 micron in diameter with the 100x objective. The extremely high photon density in the narrow laser focus creates locally-restricted, cold ablative photolysis without heating. The laser is then used to cut around the cell which drops by gravity into the RNA extraction media in the closely appositioned microcentrifuge collection tube cap. The motorized stage (128 nm stepping) is controlled by integrated Leica circuitry and software. This technique permits high yield specimen retrieval and performance is highly consistent in [name] laboratory at John Hopkins University. Using scLCM, hepatocytes are isolated in  $10 \times 10$  grids. Based on previous results, viroscapes are constructed for an average of 5 fields from each subject, totaling 500 hepatocytes, and mapped to a positional matrix (Figure 2). The data generated includes a) the proportion of infected hepatocytes; b) the magnitude of HCV infection per cell (defined as HCV RNA IU/cell [viral RNA (vRNA)]); and c) the number and depth of infected hepatocyte clusters.

[figure not shown]

Figure 2. Representative HCV viroscapes.

HCV vRNA was quantified in a grid of  $10 \times 10$  hepatocyte captures and normalized to a known standard. A map was assembled; x- and y- axes depict spatial coordinates using arbitrary units, and the amount of normalized HCV vRNA is

**High-resolution qPCR.** After capture and immediate analysis, RNA extraction is performed with the Agencourt® RNAdvance Cell v2 system that uses paramagnetic bead separation of nucleic acids, yielding high concentrations of viral and host RNAs. After extraction, specimens are divided into thirds. The first portion is tested for vRNA using the ABBOTT® RealTime HCV Assay that has been adapted for use on tissue samples (Figure 3). The second portion is used to measure 7SL, an abundant and conserved non-coding cytoplasmic RNA, using qPCR, to control for the amount of inputted RNA. 7SL is stable across hepatocytes, preventing skewing of target RNA estimates by variable cytoplasmic capture (Figure 4). Other intracellular RNAs are also quantified using the second portion. The third portion is used for Core-E1 sequencing of the HCV genome.

[figure not shown]

Figure 3. Limit of sensitivity of HCV qPCR assays tested by spiking in known amounts of HCV RNA into RNA extracted from HCV-uninfected tissues that were composed of 100 cells and subsequently serially diluted. Indicated are medians with IQR.

Additional mRNAs will be tested using stored complementary DNA (cDNA) from each captured hepatocyte. In contrast to vRNA, mRNAs often require one round of linear amplification before quantification. The Nugen WT-Ovation One-Direct system uses poly-thymidine and random hexamer priming to provide maximal coverage of coding RNAs, and is used to linearly amplify RNA non-specifically before quantification. By optimizing RNA isolation and purification, and optimizing qPCR protocols, we consistently measure viral and host RNA from ~95% of scLCM samples. We have also developed a protocol for high-resolution reverse transcription whereby we add short-length 5' and 3' adaptors to extracted RNA molecules; we then perform PCR using primers that hybridize to the adaptors, amplifying a cDNA library non-specifically from single cells. Quantitative PCR (qPCR) is performed on the library using primers and probes that are specific for target mRNAs.

High-resolution qPCR permits interrogation of the same cells for multiple pieces of data and, importantly, allows for discarding of suboptimal data (defined by insufficient amounts of a housekeeping RNA). *In situ* scLCM has the advantage of finding natural and consequently relevant determinants of HCV replication. While other methods exist to enumerate HCV-infected hepatocytes, we are not aware of another team using LCM to quantify the burden of infection per cell, nor of comparing host RNAs in infected and uninfected cells.

*Unbiased sampling and integrated image bank mapping.* Initial attempts to identify and quantify HCV-infected hepatocytes *in situ* were based on prior immunohistochemical (IHC) staining for HCV proteins, followed by dissection of HCV+ hepatocytes. These attempts were impeded by inconsistent staining, hepatic autofluorescence, and RNA loss under conventional staining protocols. We have circumvented traditional approaches by separately isolating consecutive hepatocytes prior to determining whether they are infected [5]. Pre- and post-scLCM images are stored on a secure server. After high-resolution qPCR of coded scLCM samples, virtual maps of HCV infection are assembled using stored images. The advantage of this approach is that it leverages quantitative methods, rather than competing *in situ* methods, which are semi-quantitative or even qualitative, to reveal the peaks and nadirs of HCV replication in the liver, which we have termed the viral landscape, or viroscape. The quantitative viroscape is optimally conceived for modeling applications where qualitative approaches would be inadequate. The sampling is spatially unbiased, in that hepatocytes are collected consecutively in antiparallel grids, irrespective of whether they are infected. Infection of a given hepatocyte is only determined after processing each cell separately, and operators are blinded to positional maps until final analysis. Since the minority of hepatocytes is HCV-infected, unbiased sampling permits comparisons of intracellular signals between infected hepatocytes and adjacent uninfected hepatocytes that are presumably refractory to infection despite high HCV viral loads. A linked advantage to this approach is that, rather than committing full tissue sections to interrogation of a single or small number of host mRNA molecules, each scLCM-dissected cell can be separately interrogated for multiple signals.

A key feature of the Leica LMD 6500 is that full section images are saved at low and high resolution before and after laser capture. After viral and host RNA measurements are complete,

[figure not shown]

Figure 4. RNA isolation from scLCM is consistent, and results in negligible RNA loss. qPCR in each scLCM-isolated hepatocyte against a quantitative standard (mean value is indicated by *hashed green line*) and was found to be comparable with RNA from single-cell equivalents of homogenized bulk liver tissue that was isolated by the same technique but without exposure to the laser (mean value is indicated by the *red line*). Single-cell equivalency of bulk liver homogenates was estimated by qPCR measurement of ERV3 DNA, which is an endogenous retroviral element for which two copies are found in all mammalian cells. Negative control empty isolations of equivalent volume of polyethylene naphthalate membrane were derived from the same slides and found to contain low levels of 7SL (*black dots*). A stringent threshold of 5 standard deviations over the mean negative control amount was set to avoid false quantification of cell fragments.

a positional matrix corresponding to the 10x10 dissection space is created and populated with RNA quantities. In addition, physical distances from each cell will be plotted to major hepatic structures (eg, portal tracts and centrilobular veins) that define lobular anatomy to account for differential intracellular drug concentrations and metabolism based on hepatic blood flow and lobular zones.

*Single-cell HCV Core-E1 sequencing.* The Core-E1 sequencing amplicon and cloning system is used to reliably study the diversity and evolution of the HCV quasispecies in plasma samples. The conventional Core-E1 assay uses amplification from nested PCR reactions that yield a final product of 473 bp. An advantage of this system is that it consistently produces interpretable results – the inclusion of E1 permits sufficient variability that phylogenetic distances can be calculated within subject and indeed even within a cluster of infected hepatocytes. We have adapted sensitive sequencing of the HCV Core-E1 regions from plasma to scLCM samples from tissue, and have successfully obtained sequence from hepatocytes with as low as 3 IU/cell. Core-E1 sequencing can be used to validate by an independent technique that a given cell is indeed infected. In addition, while previous studies have relied on bulk sequencing of HCV from bulk tissue, no information from such studies could be used to discriminate mechanisms of clearance of infected hepatocytes, since the resolution would be limited to the smallest unit studied. An added advantage of single-cell sequencing, through the design of separate amplicons that target different regions of the HCV genome, is in detecting drug resistant viral variants before and during DAA therapy in individual cells that may not be apparent from sequencing of the plasma quasispecies. Although no resistance is expected, core-E1 sequencing on 2-3 hepatocytes per 10x10 grid with high-level vRNA can be performed and compared between biopsies. (Sequencing all infected hepatocytes in the viroscape could be more informative, but this is beyond the resources of this study).

Intrahepatic HCV infection was studied intensively using scLCM and spatial statistical analysis in liver tissue from four subjects of the ALIVE study of injection drug users (IDUs) who had chronic genotype 1 infection. By dissecting > 1000 individual hepatocytes, the viroscape was uncovered in eleven separate grids (Figure 2), demonstrating clusters of HCV+ hepatocytes; 21-45% of all hepatocytes were infected. HCV vRNA was measured in each hepatocyte and ranged from 1 – 50 IU across all subjects with the majority of cells producing < 10 IU. This technology has been extended to allow HCV sequencing from individual hepatocytes. Moreover, IFN responses were measured in the same hepatocytes; in contrast to clustered HCV infection, a representative ISG, IFITM3, was found to have a scattered expression pattern that was neither directed toward nor away from HCV clusters. Indeed, few HCV+ hepatocytes expressed the ISG. These results suggest poor targeting of ISG expression to HCV-infected hepatocytes, and may partly explain persistence of HCV infection. Since HCV RNA amounts are the principal measures of effective DAA treatment, scLCM with high-resolution qPCR and spatial statistical analyses form a highly innovative approach to the study of intrahepatic HCV infection before and during HCV DAAs and to study the effect of HIV coinfection on the host response.

## **8.9 Post-Biopsy Clinical Evaluations**

The post-biopsy clinical evaluations will consist of vital signs and an assessment of pain at the biopsy site. Evaluations for excessive pain or bleeding will be performed within the first 4 hours after CNB1 and CNB2 by the nursing staff in the CTRC. Pain and bleeding will be principally

assessed clinically by questioning and using vital signs (heart rate and blood pressure), obtained every hour for the first 2 hours after biopsy. Subjects will be monitored for complications from liver biopsy as found on the American Association for the Study of Liver Diseases (AASLD) website:

<http://www.aasld.org/practiceguidelines/Documents/Bookmarked%20Practice%20Guidelines/Liver%20Biopsy.pdf>.

## 9.0 Adverse events

### 9.1 Non-serious adverse events

The maximum grade of all adverse events will be collected from day 0 through week 4 and documented on the case report form (CRF). At each visit, adverse effects will be ascertained. All inpatient and outpatient clinical assessments and results will be reviewed for the presence of adverse events. All patients will be evaluated by non-directed questioning for the occurrence of adverse events during the course of the study. After noting any *volunteered* adverse events, the question, "Have you had any other problems since I last saw you?" will be asked at each visit. Adverse events will then be explored through directed questioning. Standard guidelines for the management of toxicity will be closely followed to minimize risk to study participants. Adverse events will be graded according to standard clinical trial guidelines.

### 9.2 Serious adverse events

Serious adverse events will be collected from time of consent to day 0 and from week 4 to post treatment week 12.

The investigator will notify the Institutional Review Board (IRB) and the FDA of all serious adverse events in writing within 24 hours in accordance with international and local laws and regulations. Serious adverse events are defined by the International Conference on Harmonisation (ICH) as an event that:

- Results in death
- Is life-threatening
- Requires inpatient hospitalization or prolongation of existing hospitalization
- Results in persistent or significant disability/incapacity
- Is a congenital anomaly/birth defect
- Is an other important medical event (may not be immediately life-threatening or result in death or hospitalization but may jeopardize the patient or may require intervention to prevent one of the events listed above).

## 10.0 Sample Size

The anticipated sample size for analyses is 15 participants with 5 in each of three distinct groups. Group C will enroll 5 patients with HIV/HCV genotype 1a coinfection and will receive treatment with SOF/VEL representing inhibitors of HCV NS5B and NS5A a. Group A and B will

each enroll 5 patients with HIV genotype 1a mono-infection; Group A will be treated with SOF/VEL/VOX and Group B will receive only SOF/VEL representing inhibitors of HCV NS5B and NS5A only. As such, Groups B and C are treated with same two-drug DAA regimen and will permit the comparison of persons with HIV/HCV and HCV. In contrast, Groups A and B include patients with HCV mono-infection and differ by the use of the HCV NS3/4 inhibitor Voxilaprevir in Group A and will permit the comparison of the NS3/4 inhibition versus none.

Because this study is exploratory and is enrolling a very small sample, traditional statistical power calculations are not being used to justify the sample size. Instead, this sample size was developed based on the feasibility of both anticipated enrollment and the feasibility of the laboratory procedures, namely single cell laser microdissection.

For the primary outcome of difference in proportion of HCV-infected hepatocytes between week 1 and baseline, we present an approximate confidence interval around the difference in proportion within subject to show the level of precision in this exploratory single-arm study. The following assumptions are made to approximate the confidence interval in a conservative way:

- for within-subject variation – proportion of infected hepatocytes at any particular time-point is 50% (this assumption is conservative as results in maximum variation),
- the number of hepatocytes measured within each subject is 400 (this is conservative as it is estimated that between 400 and 1000 hepatocytes will be measured),
- normal approximation to the binomial for standard error estimation, and the variance of the difference will be approximated as twice the variance (assuming independence between week 1 and baseline, which is conservative except under negative correlation, which is not expected given the reported potency of the intervention being studied).

These assumptions give an estimated within-subject standard error of 0.035 for the primary outcome and can be used to formulate a confidence interval on the difference in proportions of HCV-infected hepatocytes between week 1 and baseline on a single individual. For other less conservative assumptions (larger number of hepatocytes sampled, or estimated proportion of HCV-infected hepatocytes being either larger or smaller than 0.5 at either week 1 or week 0), the within subject standard error for the difference in proportions outcome would be smaller than 0.035, and so this represents the maximum standard error for the given assay parameters that specify that at least 400 hepatocytes will be measured in each subject at each time point.

For combining the estimated differences across subjects in order to obtain a study sample estimate for the difference in proportion of HCV positive hepatocytes between week 1 and baseline, the average difference across the 5 subjects within each group will be calculated. Assuming independence across individuals, and using the above maximum within subject standard error for each of the 5 subjects gives a standard error for the average as  $0.035/\sqrt{5}$ , which is 0.015. This was obtained using conservative assumptions for the purpose of sample size considerations in this exploratory study. Therefore, the estimated maximum half-width of a two-sided 95% confidence interval on the study sample average difference in proportion is approximately  $1.96 \times 0.015 = 0.031$ .

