## 11.0 Statistical Analyses Plan:

All outcomes will be summarized and described with appropriate summary statistics. For example, estimated binomial proportions (e.g., for % of HCV-infected hepatocytes) will include 95% confidence intervals. Means, medians for continuous outcomes will include confidence

intervals and key percentiles (eg, 25th, 75th percentiles), respectively. Outcomes defined as changes will also present summary distribution of values at each time point contributing to change outcome. In addition, because of small sample size, outcomes will also be summarized on a per-subject basis for reporting. Changes will be defined as absolute differences for those outcomes where baseline distribution of proportion is close to 0 or 1, and relative (and absolute secondarily), changes otherwise. For continuous outcomes, both absolute and relative changes from baseline will be explored and summarized. Confidence intervals (using exact methods) on change outcomes will be calculated and presented.

For the primary outcome, the estimated differences will be summarized and described on a per-subject basis (i.e. 15 differences and intra-subject confidence intervals). Additionally, the proportion of infected hepatocytes will be summarized across subjects at each time point and presented. Finally, the average difference from week 0 to week 1 (absolute difference) for the study sample will be estimated and summarized.

For the plasma VK secondary outcome, longitudinal modeling will be used to combine plasma HCV viral loads (VL) over the first week. For instance, marginal modeling will focus on estimation of levels across the study sample (ie, population level inference). This can be used to describe the average change in HCV VL over the first week on treatment. In addition, (generalized linear) mixed effects models will focus on subject-specific inference (ie, prediction). Since this is a small study, these data will be graphically represented by subject.

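### The within-subject standard error of 0.035 is a maximum only if hepatocytes are independent, but cells are sampled in grids from a clustered infection

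*Combined protocol and SAP*

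**What the plan says.** Section 10.0 (Sample Size) bases its precision statement on 50% of cells infected at both visits, 400 cells per participant per visit, and "normal approximation to the binomial for standard error estimation". It states independence between the two visits and between participants. It says nothing about independence of cells within a biopsy. It notes that more cells, or a proportion away from 50%, would lower the SE, and concludes: "so this represents the maximum standard error for the given assay parameters that specify that at least 400 hepatocytes will be measured". Dividing by √5 for a group leads to the statement that "the estimated maximum half-width of a two-sided 95% confidence interval on the study sample average difference in proportion is approximately" 0.031.

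Section 11.0 (Statistical Analyses Plan) says that "estimated binomial proportions (e.g., for % of HCV-infected hepatocytes) will include 95% confidence intervals", promises "15 differences and intra-subject confidence intervals" for the primary outcome, and adds: "Confidence intervals (using exact methods) on change outcomes will be calculated and presented". Neither section mentions a design effect, grid-level variance or a spatial adjustment.

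Section 8.8 describes the sampling: "hepatocytes are collected consecutively in antiparallel grids, irrespective of whether they are infected", and "viroscapes are constructed for an average of 5 fields from each subject, totaling 500 hepatocytes". It also reports that, in four earlier subjects, infected cells lay in clusters. The hypothesis in Section 1.0 concerns clearance of such clusters, and exploratory objective 3.3.3 is to study their size and number.

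**The concern.** A binomial variance needs independent cells. If infected cells sit together and neighbouring cells are sampled as blocks, 100 cells from one grid carry less information than 100 cells drawn at random from the biopsy. The independent-cell SE is then too small by a factor of √(design effect). Exact methods do not help, because they make the same independence assumption.

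The sampling being spatially unbiased, as Section 8.8 says, concerns which cells are chosen. It does not make neighbours independent.

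At stake is the stated precision of the primary outcome. With 15 participants, the per-participant differences and their intervals are a main output. A fall to about 1% would be obvious in any case. A partial fall, which is plausible at the day 4 biopsy, or a modest difference between two people's intervals read side by side, would look more decisive than the data allow.

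**Working it through.** **Inputs.** From Section 10.0: proportion p = 0.5 at both visits, n = 400 cells, 5 participants per group, two-sided 95%. From Section 8.8: m = 100 cells per grid, so 400 cells are 4 grids; baseline infection 21–45% in earlier subjects. From Section 4.2: about 1% infected at day 7 in two participants of an earlier study. The within-grid correlation ρ is in no document. The values below are assumptions, taken as positive because infection is described as clustered.

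**1. The plan's figures.** SE = √(2 × 0.5 × 0.5/400) = 0.0354, stated as 0.035. Group SE = 0.0354/√5 = 0.0158, stated as 0.015. Half-width = 1.96 × 0.0158 = 0.031, as stated (the printed product 1.96 × 0.015 is 0.029, so the plan evidently used the unrounded value). All reproduce with independent cells.

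**2. Allowing for grids.** Design effect DE = 1 + 99ρ; SE = √(2 × 0.25/400 × DE); group half-width = 1.96 × SE/√5.

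| Assumed ρ | DE | Effective cells (400/DE) | SE, one participant | Half-width, group of 5 |
|---|---|---|---|---|
| 0 | 1.00 | 400 | 0.035 | 0.031 |
| 0.001 | 1.10 | 364 | 0.037 | 0.032 |
| 0.005 | 1.50 | 268 | 0.043 | 0.038 |
| 0.01 | 1.99 | 201 | 0.050 | 0.044 |
| 0.02 | 2.98 | 134 | 0.061 | 0.053 |
| 0.05 | 5.95 | 67 | 0.086 | 0.076 |
| 0.10 | 10.90 | 37 | 0.117 | 0.102 |

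At these inputs the break-even correlation is zero.

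**3. Slack away from 50%.** With v = [p0(1−p0) + p1(1−p1)]/n, the figure 0.0354 holds up to ρ = (0.0354²/v − 1)/99. At 400 cells this is 0.019 (21% to 1%), 0.012 (33% to 1%), 0.0095 (45% to 1%) and 0.003 (33% to an assumed 20%). At 500 cells it is 0.026 (21% to 1%) and 0.014 (45% to 1%).

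**4. Effect on conclusions, 400 cells.** At ρ = 0.10 the change from 21% to 1% is 0.20/0.069 = 2.9 SE, and from 45% to 1% it is 0.44/0.084 = 5.3 SE. A fall from 33% to an assumed 20% is 4.2, 3.4, 3.0, 2.4 and 1.7 SE at ρ = 0, 0.005, 0.01, 0.02 and 0.05.

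**5. Coverage of intra-subject intervals.** The slack in step 3 does not protect these, because they would use the observed proportions. Two simulations were run.

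- *Beta-binomial grids* (4 grids of 100 per biopsy, binomial Wald interval for the difference, 200,000 replicates). Coverage of the nominal 95% interval was about 95%, 83%, 57% and 44% at ρ = 0, 0.01, 0.05 and 0.10. It was almost the same for 50% to 50%, 45% to 1% and 21% to 1%.
- *Thresholded Gaussian spatial field* (exponential decay, correlation length 0, 0.3, 0.5, 1.0 and 1.5 cells, giving baseline DE of 1.0, 1.1, 1.5, 3.5 and 6.2). For 33% to 20%, an interval for the difference built from Clopper–Pearson limits, as a stand-in for exact methods, covered 96%, 95%, 90%, 73% and 59%. An interval from score limits at the effective cell number, with DE pooled across biopsies at the same time point, covered 95–96%. For 33% to 1% the results were 96%, 94%, 90%, 72% and 59%, against 95–96%.

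In the same simulation a correlation length of 1.0 cell gave DE 3.5 at 33% infected but 1.5 at 1%, so one DE for all time points would not serve.

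**The case against.** **The size is assumed.** This stands. Only the direction is firm, given positive average correlation within grids.

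**The larger SEs stack worst cases.** The table combines clustering with 50% at both visits and the minimum cell count. For 33% to 1% with the average of 500 cells, the SE is 0.030, 0.037 and 0.052 at ρ = 0.01, 0.02 and 0.05, so 0.035 survives weak clustering. This is fair as regards the number 0.035. It does not rescue the intra-subject intervals.

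**The wording is qualified, and the interval method is not named outright.** Section 10.0 calls its interval approximate and ties the maximum to assay parameters. Section 11.0 gives binomial intervals as an example and exact methods for changes in general. Binomial or exact is nevertheless the natural reading, especially as Section 10.0 offers 0.035 for a single individual's interval. Section 8.8 does mention spatial statistical analysis, but does not link it to the primary interval.

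**Between-group tests are unaffected.** The rank tests in Section 11.0 use one value per participant and do not assume independent cells. This stands.

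**The proposed remedy is imperfect.** Correcting 0.031 for clustering still leaves out between-participant variation in the change; an assumed SD of 0.10 would alone give 1.96 × 0.10/√5 = 0.088. Pooled design effects give the right coverage on average, not for each person: by normal approximation, a pooled DE of 3.5 gives about 86% coverage for someone whose true value is 6.2 and over 99% for someone at 1.5. For a 1% biopsy alone, the pooled interval over-covers slightly (about 97–98%).

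**Conclusion.** The concern holds. The arithmetic behind 0.035 is right, but it is a maximum only over cell number and proportion with independent cells. The protocol's own sampling scheme and findings speak against that independence. At the plan's inputs, any positive within-grid correlation exceeds it: by about 40% in the SE at ρ = 0.01 (0.050) and by a factor of about 2.4 at ρ = 0.05 (0.086). With very weak clustering the excess is small. Intra-subject intervals that ignore grids lose coverage at realistic proportions too.

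The intervals are descriptive, the sample size is justified by feasibility, and a fall to about 1% would remain evident. The point should be fixed, but it does not undermine the design.

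**What to change.** In Section 10.0, delete the word maximum, or make it explicitly conditional on independent cells. State SE = 0.035 × √DE with DE = 1 + 99ρ over a range of assumed ρ, and carry that range through to the 0.031 half-width. Say that the half-width covers measurement error only and excludes variation between participants.

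In Section 11.0, name the intra-subject interval and make it allow for grids. One workable form:

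- Estimate a design effect (or beta-binomial overdispersion) pooled across biopsies, separately for baseline, day 4 and day 7, and floor it at 1.
- Use cells divided by the design effect as the effective number in a score-type or exact interval.
- Do not rely on a t interval from one biopsy's grids alone; with 4–5 grids and about 1% infected it is unstable.
- Report the estimated design effects beside the intervals.

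The cost is a little more analysis. Grid positions are already recorded, and no extra participants, biopsies or assays are needed. The intervals will be wider. Pooling assumes broadly similar clustering across people at the same time point. When clustering, baseline proportion and grid number varied between people in simulation, average coverage was still about 94%, against about 74% when grids were ignored.
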